8.1.6. Cochran-Mantel-Haenszel Test for Proportions

A Cochran-Mantel-Haenszel (CMH) will be used as a test of proportions. For the overall, and analyses by dose(placebo vs 20 mg and placebo vs 80 mg), a Cochran-Mantel-Haenszel test for proportions stratified by TTR genotype and NYHA baseline severity (NYHA Classes I and II combined and NYHA Class III) will be used. For subgroup analysis by TTR genotype, a CMH test for proportions stratified by NYHA baseline severity will be used. The analysis will also be performed separately by Baseline severity using a CMH test for proportions stratified by TTR genotypes (variant and wild-type).

8.2. Statistical Analyses

The number of subjects screened, randomized to the double-blind treatment phase, and completing the study will be summarized. The reason for all discontinuations will be summarized by treatment group. Baseline demographic and other characteristics, including the frequency of specific genotypes will be tabulated for the ITT population. Quantitative variables will be described by standard descriptive statistics (mean, standard deviation, minimum, and maximum), and qualitative variables will be summarized by frequency tables.

Concomitant medications including their preferred term and therapeutic subgroup will be summarized by treatment groups.

The primary analysis and key-secondary endpoints will be analyzed using both ITT and PP Analysis Sets. All other efficacy analyses will be performed on ITT Analysis Set only.

8.2.1. Primary Analysis

The primary analysis uses a hierarchical combination of all-cause mortality and frequency of cardiovascular-related hospitalizations (which is defined as the number of times a subject is hospitalized [ie, admitted to a hospital] for cardiovascular-related morbidity) over the duration of the trial as described in [Section 8.1.1](#). The primary analysis will combine the subjects in the tafamidis 20 mg and tafamidis 80 mg groups (including subjects in 80 mg group that may have had a dose reduction to 40 mg) into one pooled group. This pooled group (tafamidis) will be compared with the placebo group using the Finkelstein-Schoenfeld method ([Finkelstein 1999](#)).

8.2.2. Key-Secondary Analyses

The key secondary endpoints listed below will be evaluated using a mixed model repeated measures ANCOVA detailed in [Section 8.1.3](#).

1. Change from Baseline to Month 30 in distance walked during the 6MWT;
2. Change from Baseline to Month 30 in KCCQ Overall score.

To maintain the type I error rate at or below the specified level, a pre-specified hierarchical order for testing as indicated above will be used to maintain the overall alpha at 0.05 for these two key secondary endpoints. The multiplicity procedure will be applied to the ITT analysis set only.

Statistical significance of the key-secondary analyses is dependent on first achieving statistically significant results in the primary analysis. In this hierarchical approach of key-secondary endpoints, the change from Baseline to Month 30 in distance walked during the 6MWT is first tested at the 0.05 level. If the p-value for the test of 6MWT is ≤ 0.05 , the 2nd variable in the list, the change from Baseline to Month 30 in KCCQ Overall Summary score will be tested at the 0.05 level. If the p-value of the test for 6MWT is > 0.05 , then statistical significance cannot be achieved for the subsequent test on KCCQ.

Supplemental analyses of the two key secondary variables will be performed to support the robustness of the conclusions drawn. The pattern-mixture analysis will group the subjects on the basis of their dropout or missing-data patterns. 'Patterns' will be defined under the following two cases:

Case 1:

Pattern 1A - all subjects who have provided the key-secondary endpoint (each done separately) data for month 30.

Pattern 1B - all subjects who have not provided the key-secondary endpoint data for month 30.

Case 2:

Pattern 2A - all subjects who have the key-secondary endpoint data (each done separately) for month 15 or beyond.

Pattern 2B - all subjects who do not have key-secondary endpoint data beyond month 15.

The pattern mixture analysis will use a mixed model repeated measures ANCOVA (MMRM) with an unstructured covariance matrix (or as appropriate); center and subject within center as random effects; treatment, visit, TTR genotype (variant and wild-type), pattern, visit by treatment interaction, and treatment by pattern interaction as fixed effects and baseline score as covariate. Sample SAS code is provided in [Appendix 1.3](#).

Exploratory analyses of the key secondary endpoints will include results from the MMRM analysis at each individual time point other than month 30.

Additional exploratory analyses of the key secondary endpoints will include results from the MMRM analysis at each individual time point by dose group (randomized dose group), TTR genotype (variant and wild-type), and NYHA baseline classification. Descriptive statistics overall, by dose, by TTR genotype, and by NYHA baseline classification will be provided for each time point.

Except for the analyses by dose, all analyses of the key-secondary endpoints, including the proposed exploratory analyses of these endpoints will compare the pooled tafamidis group with the placebo group.

8.2.3. Secondary Analyses

The "cardiovascular -related mortality" in all analyses, unless otherwise specified, will combine deaths adjudicated as cardiovascular-related with deaths adjudicated as indeterminate.

The cardiovascular-related mortality and all-cause mortality will be analyzed using survival analysis methods detailed in [Section 8.1.2](#).

Frequency of cardiovascular-related hospitalizations will be analyzed using the Poisson regression analyses detailed in [Section 8.1.5](#).

All the analyses on the secondary endpoints described above will additionally be presented by TTR genotype (variant and wild-type), NYHA baseline classification as well as dose (randomized dose group) and will be considered exploratory.

The proportion of subjects who achieved TTR stabilization in each treatment group at Month 1 will be compared using a Cochran-Mantel-Haenszel test detailed in [Section 8.1.6](#).

A similar test of proportion will be done on TTR stabilization at all other time points and considered exploratory. No subgroup analyses will be done at these other time points.

Except for the analyses by dose group, all analyses of the secondary endpoints, including the proposed exploratory analyses of these endpoints will compare the pooled tafamidis group with the placebo group.

8.2.4. Exploratory Analyses

A supplemental analysis, repeating the methodology of the primary analysis, will only include hospitalizations adjudicated as cardiovascular related and exclude hospitalizations adjudicated as "indeterminate". *To examine the potential effect of including heart transplantation or cardiac mechanical assist device as "deaths" in the primary analysis, a sensitivity analysis will be performed treating all transplantation or cardiac mechanical assist device in the same manner as any other censored observation. As an additional sensitivity analysis, a multiple imputation analysis will be applied using the method developed by Rubin ([Rubin 1987](#)). Combined results will be provided for the primary analysis (ie, using Finkelstein-Schoenfeld) as well as for the separate mortality and morbidity elements. Details are provided in [Appendix 1.4](#).*

An exploratory analysis, using the methodology of the primary analysis, will be repeated by the dose group to which subjects were randomized (tafamidis 20 mg vs placebo and tafamidis 80 mg vs placebo) to explore the effect by dose group.

Exploratory analysis of the secondary endpoint, all-cause mortality will be done by treating all heart transplantation or cardiac mechanical assist device in the same manner as any other censored observation. Exploratory *subgroup analysis using the Finkelstein-Schoenfeld method comparing the pooled tafamidis group and the placebo group, similar to that of the primary analysis, will also be done by the TTR genotype (variant type and the wild-type) and Baseline severity (NYHA Classes I and II combined and NYHA Class III) status.*

To examine the potential effect of region, the primary analysis will be repeated with the inclusion of a factor for region. More specifically, the test statistic will be stratified by TTR genotype (variant and wild-type), baseline severity category (NYHA Classes I and II combined and NYHA Class III), and region (US and Ex-US).

Frequency of All-cause hospitalization will be analyzed using the Poisson regression analyses detailed in [Section 8.1.5](#).

Cardiovascular-related days hospitalized, and all-cause days hospitalized will be analyzed using an analysis of variance (ANOVA) detailed in [Section 8.1.4](#).

An exploratory analysis based on the Finkelstein-Schoenfeld method similar to that of the primary analysis detailed in [Section 8.1.1](#) will be done for combination of variables listed below:

- All-cause mortality and frequency of all-cause hospitalizations,
- All-cause mortality and cardiovascular-related days hospitalized using the Finkelstein-Schoenfeld analysis,
- Cardiovascular-related mortality and frequency of cardiovascular-related hospitalization using the Finkelstein-Schoenfeld analysis.

The exploratory endpoints listed below will be evaluated at each time point post-baseline using a mixed model repeated measures ANCOVA (MMRM) as detailed in [Section 8.1.3](#).

- Change from Baseline in Kansas City Cardiomyopathy Questionnaire: (KCCQ) domain scores (Physical limitation, Symptom stability, Symptom frequency, Symptom burden, Total symptom, Self-efficacy, Social limitation, and Quality of life) and clinical summary score,
- Change from Baseline in EuroQoL-5 Dimensions (EQ-5D-3L) Index Score and visual analog scale (VAS) scores,
- Patient Global Assessment,
- Change from Baseline in Modified Body Mass Index,

- Change from Baseline in NT-proBNP concentration,
- TTR oligomer concentration at each time point,
- TTR concentration at each time point,
- Change from Baseline in echocardiographic parameters:
 - End-diastolic interventricular septal wall thickness (mm),
 - Left ventricle posterior wall thickness (mm),
 - Left ventricular ejection fraction (%),
 - Left ventricular stroke volume (mL),
 - Global longitudinal strain,
 - Circumferential strain mid global,
 - Radial strain mid global.

All other echocardiographic parameters listed as endpoints in [Section 6.1.4](#) will be analyzed descriptively.

The TTR oligomer concentration and TTR concentration will additionally be analyzed by dose. Descriptive statistics are presented by visit for the NYHA Classification (Class I, II, III, and IV). The number and percent of subjects with an improvement (decrease by at least one classification), those who worsened (increase by at least one classification), and those with no change (same classification) from baseline are presented at each visit using a shift table. A cross-tabulation of baseline severity level and post baseline change level will be presented at each visit for Patient Global Assessment scale.

Plasma concentrations of tafamidis will be summarized with descriptive statistics (n, arithmetic mean, standard deviation, coefficient of variation, geometric mean, median, and minimum and maximum) by dose, visit, and nominal time.

Plasma concentrations of diflunisal will be provided as listings by visit.

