The transthyretin (TTR) % stabilization data from Study B3461040 (Figure 1) suggest that a plateau is achieved as the molar ratio of tafamidis: TTR plasma concentration (MR) increases. Based upon the data available prior to conducting Study B3461040, it was believed that exposures achieved following a tafamidis dose of 20 mg once daily (QD) were sufficient to approach the TTR % stabilization plateau. The data from Study B3461040 suggest that doses higher than 20 mg provide a greater degree of stabilization, as measured by the urea-based TTR stabilization assay. While the long-term risk-benefit of doses higher than 20 mg QD is unknown, it is reasonable to postulate that greater TTR stabilization has the potential to provide additional efficacy.

In order to calculate molar ratios at various tafamidis exposures, a TTR concentration must be assumed. Mean TTR concentrations observed at Baseline in Study Fx-005 (24.7 mg/dL) and in patients with V122I mutations in Study Fx1B-201 (13.5 mg/dL) and the Transthyretin Amyloid Cardiac Study (TRACS) (14.9 mg/dL) are assumed for the calculations that follow: a 20 mg QD tafamidis dose at steady state produces a mean MR in the range of 1.2 to 3.2 from mean minimum concentration at steady state (C_{min,ss}) to maximum concentration at steady state (C_{max,ss}), which is below the plateau region of the data depicted in (Figure 1).

Mean $C_{min,ss}$ to $C_{max,ss}$ following tafamidis doses of 80 mg are expected to produce MR values of 3.5 to 9.6, which are approaching or on the plateau region of TTR % stabilization.

Figure 1. Scatter Plot of TTR Percent Stabilization vs Tafamidis:TTR Molar Ratio by Treatment in Study B3461040

Abbreviations: TTR= transthyretin; QD = once daily
Source: B3461040 CSR Figure 14.4.7.2.1

Based upon the TTR % stabilization data, tafamidis doses of 20 and 80 mg will be used in Study B3461028. The 20 mg dose will provide additional safety and efficacy data for that previously studied dose in TTR-FAP. The 80 mg dose is approaching maximal TTR % stabilization, which has the potential for increased efficacy over the 20 mg dose.

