9.1. Sample Size Determination

The primary comparison of interest is the pooled tafamidis 20 mg and 80 mg treatment groups vs. placebo. The target sample size is 400 subjects.

A sample size of 400 subjects is based on findings from study Fx1B-201 (a 12-month, open-label study of tafamidis in TTR-CM subjects), TRACS (an observational study with no treatment intervention other than standard of care in TTR-CM subjects), an understanding of current clinical outcomes in this population, and the uncertainty of the assumptions derived from these limited data.

Given that no closed-form sample size estimation solution is available for the primary analysis method, sample size estimation was performed based on simulations.

Sample size assumptions include:

1. All-cause mortality rate of 12.5% for the tafamidis group and 25.0% for the placebo group (ie, a 50% reduction in mortality with treatment).
2. 1.5 cardiovascular-related hospitalizations for the tafamidis group and 2.5 cardiovascular-related hospitalizations for the placebo group.
3. Treatment duration of 30 months.
4. Significance level (alpha) of 0.05 (two-sided test).

With these assumptions, 300 subjects (n=120 for placebo, n=60 for 20 mg, n=120 for 80 mg) yields a power of over 90% for the primary comparison. A more conservative assumption of 30% reduction in mortality (17.5 % for tafamidis and 25% for placebo) yields a power of approximately 80%. With an assumption of 30% reduction in mortality and increasing the number of subjects to 400 subjects (n=160 for placebo, n=80 for 20 mg, and n=160 for 80 mg) yields a power of approximately 90%.

Summary of operating characteristics:

| Assumptions | Sample Size | Power |
|--|--------------------|--------------|
| 50% mortality reduction, hosp frequency 2.5 (pbo), 1.5 (taf) | N=300 | 96% |
| 30% mortality reduction, hosp frequency 2.5 (pbo), 1.5 (taf) | N=300 | 80% |
| 30% mortality reduction, hosp frequency 2.5 (pbo), 1.5 (taf) | N=400 | 90% |

pbo=placebo, taf=tafamidis

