2.2. Study Objectives

The primary objective of this study is to assess the efficacy of an oral dose of 20 mg or 80 mg tafamidis meglumine soft-gel capsules based on all-cause mortality and on frequency of cardiovascular-related hospitalizations as well as to assess safety and tolerability in comparison to placebo. Tafamidis or placebo will be administered once daily, in addition to standard of care, for 30 months in subjects diagnosed with variant or wild-type TTR cardiomyopathy (TTR-CM).

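### The objective names two doses but the alpha-controlled sequence contains no dose-level test; appending the planned by-dose tests after KCCQ-OS would take nothing from any existing test.

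*SAP*

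**What the plan says.** The primary objective (Protocol 2.1, SAP 2.2) is to "assess the efficacy of an oral dose of 20 mg or 80 mg tafamidis meglumine soft-gel capsules" against placebo. Protocol 9.1 then fixes the comparison: "The primary comparison of interest is the pooled tafamidis 20 mg and 80 mg treatment groups vs. placebo". SAP 8.2.1 carries this through: "The primary analysis will combine the subjects in the tafamidis 20 mg and tafamidis 80 mg groups".

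For the key secondaries, SAP 8.2.2 states that "a pre-specified hierarchical order for testing as indicated above will be used to maintain the overall alpha at 0.05". The controlled order is the primary analysis, then 6MWT, then KCCQ-OS. All three use the pooled group, and nothing follows.

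The separate doses appear in SAP 8.2.4: "An exploratory analysis, using the methodology of the primary analysis, will be repeated by the dose group to which subjects were randomized". Protocol 9.4 says the same. By-dose analyses of the key secondaries, mortality and hospitalization are also exploratory (Protocol 9.2.2 and 9.3; SAP 8.2.2 and 8.2.3). TTR stabilization by dose has no alpha control either, because the Protocol Summary places the secondary endpoints outside the alpha-conserving strategy.

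The protocol does not present the doses as interchangeable. In Protocol 1.2 the expected tafamidis:TTR molar ratio at 20 mg is 1.2 to 3.2, a range "which is below the plateau region of the data depicted in" Figure 1. At 80 mg it is 3.5 to 9.6, expected to be at or close to that plateau.

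**The concern.** A significant pooled test rejects the hypothesis that neither dose does anything. It does not say which dose is responsible. The pooled contrast also describes a 1:2 mixture of 20 mg and 80 mg, set by the allocation, which no subject receives. The objective names the doses, the dose-level data are randomized, and the by-dose analyses are already specified. Yet no outcome of the trial as planned allows an error-controlled statement about either dose. The alpha that survives a successful KCCQ-OS test goes unused.

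**Working it through.** **Inputs.** Protocol 9.1 gives 30-month mortality of 25% on placebo and 12.5% (50% reduction) or 17.5% (30% reduction) on tafamidis, mean cardiovascular hospitalizations of 2.5 and 1.5, two-sided alpha of 0.05, and stated powers from simulation. The target arms are 160 placebo, 80 on 20 mg and 160 on 80 mg. The documents give no count distribution, no dropout rate, no per-dose power and no power for 6MWT or KCCQ-OS.

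**Step 1: reproduce the stated power.** The statistic T/√V of SAP 8.1.1 was simulated with exponential death times, no dropout, one stratum, and counts independent of death. The count distribution had to be assumed.

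| Counts | N=300, 50% | N=300, 30% | N=400, 30% |
|---|---|---|---|
| Protocol 9.1 | 96% | 80% | 90% |
| Poisson | 100% | 99.7% | 100% |
| Gamma-Poisson, dispersion 1.0 | 97.2% | 84.9% | 93.3% |
| Gamma-Poisson, dispersion 1.25 | 95.8% | 80.1% | 90.5% |
| Gamma-Poisson, dispersion 1.5 | 94.3% | 75.8% | 87.1% |

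Dispersion 1.25 matches all three stated figures and is used below. With four assumed strata the N=400 figure is 87.5%.

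**Step 2: what a pooled win says about one dose.** Power of 90% corresponds to a noncentrality of 1.960 + 1.282 = 3.242. If 20 mg has a fraction f of the 80 mg effect, the pooled noncentrality is 3.242 × (160 + 80f)/240.
- f = 0.5: 3.242 × 200/240 = 2.702, power Φ(2.702 − 1.960) = 77%.
- f = 0: 3.242 × 160/240 = 2.161, power Φ(0.201) = 58%. Simulation gives 57.5% (62.2% to 53.5% over dispersion 1.0 to 1.5).

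**Step 3: each dose alone, equal effects, no gate.** Scale 3.242 by √[(1/240 + 1/160)/(1/a + 1/b)].
- 80 mg, 160 vs 160: 3.242 × √(0.010417/0.0125) = 2.959, power 84%.
- 20 mg, 80 vs 160: 3.242 × √(0.010417/0.01875) = 2.416, power 68%.

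These are not the powers of the proposed tests, which are gated.

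**Step 4: gated power (simulated, 30% reduction, N=400).** Requiring the pooled primary to succeed as well:
- 80 mg: 82.8% (87.6% to 78.5% over dispersion 1.0 to 1.5).
- 20 mg after 80 mg: 60.5% (67.0% to 55.3%).
- 20 mg in parallel with 80 mg: 66.3% (71.6% to 61.8%).

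Pooled power stays at 90.2% in this run. If 6MWT and KCCQ-OS each had 70% to 90% power and were independent (assumption), both would pass 0.7² = 49% to 0.9² = 81% of the time. Then:
- 80 mg: 0.828 × 0.49 = 41% to 0.828 × 0.81 = 67%.
- 20 mg after 80 mg: 0.605 × 0.49 = 30% to 0.605 × 0.81 = 49%.

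**Step 5: error control.** Tests at the end of a fixed sequence cannot change any earlier decision. If both dose nulls are true, the pooled null is true, so the first gate opens at most 5% of the time. If one dose null is true, its test runs at 0.05. No split between the doses is needed. In simulation, with both key secondaries taken as always passing (the worst case for error), the chance of any false dose claim under the global null is 4.3%, against 9.3% without the pooled gate. When only 80 mg works, 20 mg is falsely claimed 2.6% of the time; in the reverse case the figure is 2.5%.

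**The case against.** The pooling is a disclosed choice. Protocol 9.1 names the pooled comparison and builds the power on it, the hypotheses in SAP 4.1 compare tafamidis with placebo, the Protocol Summary states the aim at drug level, and Protocol 1.2.2 gives the 80 mg arm an exploratory purpose. Dose results are already planned, so only their confirmatory status is missing. All of this stands. A reader might infer that the plan contradicts its own objective, or that the objective promises two confirmatory dose claims. The documents do not support that, because naming both doses can equally describe the regimens given.

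The inert-20 mg case is also extreme. Fx1B-201, which gave 20 mg, fed the sample-size assumptions. Protocol 1.2 reports TTR stabilized in 34 of 35 subjects at Week 6, and Protocol 1.2.1 reports about 87.5% survival at 30 months from diagnosis. Being below the plateau is not being inactive, so 58% is a bound and not a forecast.

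Finally, the new tests sit behind three gates. If 20 mg is weak, the pooled key secondaries are diluted too, so the dose tests are hardest to reach when they matter most. This limits the benefit but adds no cost.

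**Conclusion.** The point holds as a free improvement. Under the current plan, full success on every controlled test supports only the statement that at least one dose differs from placebo. Placing the by-dose tests last would allow an error-controlled statement on a dose, with familywise error at or below 5% and no loss to any earlier test. That alpha argument depends on no modelling assumption. The power figures do: they rest on gamma-Poisson counts with dispersion 1.25, equal dose effects, a 30% mortality reduction and N=400, and the fully gated ranges also rest on assumed, independent pass rates for 6MWT and KCCQ-OS.

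Two further inferences should be resisted. The change does not rescue a pooled primary that fails because 20 mg dilutes 80 mg, since the chain then stops at its first step. And the 84% and 68% of step 3 should not be quoted as the power of the added tests.

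**What to change.** Before unblinding, extend the fixed sequence in SAP 8.2.2 and Protocol 9.2.2. After a significant KCCQ-OS result, test each dose against placebo with the stratified Finkelstein-Schoenfeld method on the ITT set, each at two-sided 0.05. Either test 80 mg and then 20 mg, or test both in parallel. The serial order follows arm size only (160 against 80) and is not a view on which dose is right. The parallel form is equally valid and gives 20 mg slightly more power. State the gated power with its assumptions, and say in SAP 8.2.4 and Protocol 9.4 that the by-dose tests stay exploratory if any gate fails.

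The cost is a few sentences. The analyses are already specified, although the documents do not show that they are programmed. SAP section 1 records the study as ongoing and blinded, and Protocol section 9 requires a protocol amendment only for major changes to the primary endpoint or its analysis, which this is not. Placing the dose tests directly after the primary would avoid the 6MWT and KCCQ-OS gates, but it would cost those endpoints power and so would not be free.

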1. AMENDMENTS FROM PREVIOUS VERSION(S)

- **Status of study when amendment made:**

Study is ongoing and remains blinded.

- **Details of Changes and Rationale:**

Amendment 1 (SAP Version 2)

Section of the SAP	Summary of change	Rationale
Various sections	Typographical corrections and clarifications For example: Changed “patients” to “subjects” for consistency.	Corrected minor typographical errors and inconsistent terminology.
2.1 Study Design	
 • Clarified specification of sample size as 400 subjects. • Specified the duration of 30 months to be equal to 910 days. 	Inserted new text from protocol amendment 1.
5.6.2. Deviations Assessed Post Randomization	Added use of 3 prohibited medications, ie, diflunisal, tauroursodeoxycholate, and doxycycline as criteria for exclusion from Per-Protocol Analysis Set.	Use of prohibited medication as described in protocol amendment 1 Section 5.8.1. Contraindicated Therapies.
6.1.4. Exploratory Endpoints	Added echo strain and other parameters.	Inserted new text from protocol amendment 1.
8.1.1. Finkelstein Schoenfeld Analyses	
 • Clarified text around algorithm involving “censored” subjects. • Removed sentence related to analysis of “indeterminate” events. 	
 • Modified text to improve clarity. • Removed sentence regarding analysis of events adjudicated as “indeterminate” as it was inconsistent with the last sentence of the first paragraph of Section 8.1.1.
8.2.2. Key Secondary Analyses	Added specification of pattern mixture analysis as a supplemental analysis of the key-secondary analyses.	Inserted new text per agreement with FDA.
8.2.3. Secondary Analyses	Added a statement describing the handling of deaths adjudicated as “indeterminate” similar to the handling of “hospitalizations”.	Added missing detail for handling “indeterminate” deaths in the analysis.
8.2.4. Exploratory Analyses	
 • Added analysis of placebo vs 80 mg randomized subjects who were not downtitrated as requested by PMDA. • Added analysis by region as requested by FDA. • Added additional exploratory endpoints. 	
 • Added analysis requested by PMDA and FDA. • Added exploratory endpoints to be consistent with protocol amendment 1.

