The term “censored” refers to a subject who discontinues from the trial for reasons other than death. For such subjects, there will be additional follow-up to obtain vital status (and transplant status / cardiac mechanical assist device status) at Month 30 and that information will be used in the analysis. In the case where one subject is censored before a second subject has died, and where the vital status of the first patient at Month 30 is missing, then the frequency of cardiovascular-related hospitalizations at the shorter of their follow-up times (the shorter of the 2 subjects’ study participation) will be used in assigning a +1 or -1. In the simpler case where one subject drops out but both are known to be alive at Month 30, the frequency of cardiovascular-related hospitalizations, at the shorter of their follow-up times (the shorter of the 2 subjects study participation), will be used in assigning a +1 or -1. Comparisons of cardiovascular related hospitalization frequency for subjects who completed all 30 months study duration will be based on the earlier of the two actual study durations (days).

Subjects, who discontinue for transplantation (ie, heart transplantation and combined heart and liver transplantation) or for implantation of a cardiac mechanical assist device, will be handled in the primary analysis in the same manner as death. More specifically, the time of the transplant or cardiac mechanical assist device implant will be used in the subject-to-subject comparison in the same manner as if the subject had died at that time (regardless of any additional vital status follow-up information). Data from subjects who drop out for a liver-only transplantation will be handled in the same manner as the data from all other censored subjects.

The proposed test is a score test based on the sum of the scores for the treated group. A value of $D_i = 1$ for subjects in tafamidis and $D_i = 0$ for subjects in the placebo group. Using the u_{ij} for every pair of subjects defined above, we assign a score to each subject.

The subjects are divided into 4 strata $k = 1; 2; 3, 4$. If A_k is the set of indices of the n_k subjects in the k^{th} strata and that U_i is calculated within strata (for $i \in A_k; U_i = \sum_{j \in A_k} u_{ij}$), then the test statistic is based on

$$T = \sum_k \sum_{i \in A_k} D_i U_i$$

Let m_k be the total number of subjects in the k_{th} stratum who are in the tafamidis group. Then in k_{th} strata

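### The region analysis in SAP 8.2.4 adjusts for region but cannot show whether the treatment effect differs between US and ex-US subjects

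*SAP*

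**What the plan says.** SAP 8.2.4 (Exploratory Analyses) states the purpose and the method together: "To examine the potential effect of region, the primary analysis will be repeated with the inclusion of a factor for region". The next sentence specifies it: "More specifically, the test statistic will be stratified by TTR genotype (variant and wild-type), baseline severity category", and the list of factors closes with "and region (US and Ex-US". The amendment table in SAP section 1 gives the origin: "Added analysis by region as requested by FDA". I use that entry only for where the analysis came from.

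SAP 8.1.1 defines the statistic: "The proposed test is a score test based on the sum of the scores for the treated group". Scores are formed within strata and summed over strata into one T with one variance V, and T/√V is compared with the normal distribution. Adding region turns 2 × 2 = 4 strata into 2 × 2 × 2 = 8. The output is still one Z.

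The other factors get separate results. SAP 8.2.4 says the Finkelstein-Schoenfeld subgroup analysis "will also be done by the TTR genotype (variant type and the wild-type) and Baseline severity", 8.1.1 says how each of these is stratified, and the test is also repeated by dose. Table 2 has columns for dose, genotype and NYHA class but none for region. Protocol 9.4 lists no region analysis.

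**The concern.** The trial is international, so a reader will want to know whether the benefit appears both inside and outside the US. The only analysis that mentions region says it looks at the effect of region, yet its method compares subjects within region and then adds everything up. Any difference between the two regional effects is averaged away before a result is seen.

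Two things are at stake. The question has no pre-specified answer, so a regional breakdown added after unblinding would be post hoc. And a significant region-stratified Z could later be cited as evidence that the effect holds across regions, which it cannot show.

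**Working it through.** **Inputs from the documents.** N=400, 160 placebo against 240 pooled tafamidis; two-sided alpha 0.05; 30 months; 25% placebo mortality against 17.5% (30% reduction) or 12.5% (50% reduction); 2.5 against 1.5 cardiovascular hospitalizations (protocol 9.1). T and V are as in SAP 8.1.1.

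**Assumptions, because the documents give no figures.** US share 40% to 70%; 50% variant and 30% NYHA III; exponential death times; hospitalization counts proportional to time alive; no dropout; gamma-Poisson overdispersion chosen as below. There were 1,000 to 4,000 simulated trials per setting.

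**Step 1: the plan's own power.** Protocol 9.1 states 96%, 80% and 90% for N=300 with 50% reduction, N=300 with 30% and N=400 with 30%.

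| Counts | N=300, 50% | N=300, 30% | N=400, 30% |
|---|---|---|---|
| Protocol | 96% | 80% | 90% |
| Poisson | about 100% | 99.8% | 99.9% |
| Dispersion 0.5 | 98% | 91% | 97% |
| Dispersion 1.0 | 95.8% | 80.9% | 89.7% |
| Dispersion 1.5 | 91% | 71% | 84% |

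Dispersion 1.0 reproduces all three within 2 points and is used below.

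**Step 2: what the eight-stratum test keeps.** Group the strata by region: T = T_US + T_ex and V = V_US + V_ex, so

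Z = (T_US + T_ex) / √(V_US + V_ex).

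Only the sum enters. T_US = T_ex = t and T_US = 2t, T_ex = 0 have the same numerator. The difference, which is what shows a regional effect, is discarded.

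**Step 3: simulation at 50% US.** Tafamidis rates are deaths/admissions; placebo is 25%/2.5 throughout. The contrast is the difference in net benefit per pair, US minus ex-US.

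| Scenario | Mean Z, 8 strata | Significant | US alone | Ex-US alone | Contrast significant |
|---|---|---|---|---|---|
| A. Uniform 17.5%/1.5 | 3.22 | 89.9% | 64% | 63% | 4% |
| B. US-only 12%/0.75 | 3.25 | 90.0% | 99.8% | 5% | 91% |
| C. Uniform, weaker, 21.25%/1.95 | 1.56 | 34.8% | 20% | 21% | 5% |
| D. US-only 17.5%/1.5 | 1.63 | 37.1% | 63% | 5% | 36% |

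A and B cannot be told apart by Z, nor can C and D. The region-specific columns separate both pairs.

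**Step 4: hand check.** With equal regions, Z ≈ (Z_US + Z_ex)/√2 and contrast ≈ (Z_US − Z_ex)/√2.

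- A: each region has mean 3.22/√2 = 2.28; power Φ(2.28 − 1.96) = Φ(0.32) ≈ 63%.
- B: Z_US = 3.25 × √2 = 4.60 and Z_ex = 0; contrast 4.60/√2 = 3.25, power Φ(1.29) ≈ 90%.
- D: Z_US = 2.28 and Z_ex = 0; pooled and contrast are both 2.28/√2 = 1.61, power Φ(−0.35) ≈ 36%.

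These agree with the table.

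**Step 5: other US shares.** At 60% US, a uniform effect gives mean Z 3.18 (88.9%) and a matched US-only effect (16%/1.1) gives 3.12 (88.3%); the contrast is significant in 4% and 60%. For a US-only effect of planned size the contrast reaches 37% at 60% US and 31% at 70% US; a second simulation gave 39% at 50% US and 33% at 65% US.

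**The case against.** The strongest defence is that the planned analysis is a legitimate one. Restricting comparisons to subjects from the same region asks whether the primary result survives adjustment for regional differences such as admission practice, and the test answers that. SAP 8.2.4 sets no pass criterion and makes no claim of consistency. The regulator's request is not in the documents, so it cannot be established whether adjustment or separate results were wanted. All of this stands, and it is why the test should be kept. It does not supply a regional result, and the stated purpose invites a reader to expect one.

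A second defence is that a regional contrast is weak. This also stands. The 91% in scenario B needs a US effect of (25 − 12)/25 = 52% on mortality and (2.5 − 0.75)/2.5 = 70% on admissions, against at most 50% and (2.5 − 1.5)/2.5 = 40% in protocol 9.1. At planned size, power is about a third. That is a reason to lead with estimates and intervals, not a reason to omit them.

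Third, the analysis is exploratory and region is not a randomization stratum. That limits how much this matters; it does not remove the gap.

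**Conclusion.** The point holds in this form: the planned analysis adjusts for region and cannot show whether the effect differs between US and ex-US. The algebra in Step 2 depends on no assumption. The sizes (3.22 against 3.25, and 1.56 against 1.63) rest on the assumed 50% US share, dispersion 1.0 and stratum mix.

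Three stronger readings are tempting and are not supported.

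- **That the test returns the same answer whatever the regional pattern.** This is true only when the pooled effects are equal. If the effect keeps its planned size in the US and vanishes elsewhere, mean Z falls from 3.22 to 1.63. Power falls from 89.9% to 37.1% at 50% US, from 89.2% to 16.3% at 40% US, and from 88.7% to 74.0% at 70% US. The fall still cannot be read as a regional effect, because a weaker uniform effect looks the same.
- **That comparing the four- and eight-stratum results reveals heterogeneity.** They can differ: for the matched US-only effect at 60% US, power is 80.2% and 88.3%. The unweighted sum gives larger strata more weight, so this shift is not an interpretable test.
- **That the primary conclusion or the type I error is affected.** Neither is.

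This is a worthwhile, inexpensive correction to an exploratory analysis.

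**What to change.** In SAP 8.2.4:

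1. Keep the region-stratified test and describe it as a region-adjusted sensitivity analysis of the primary result.
2. Add exploratory Finkelstein-Schoenfeld analyses within US and within ex-US subjects, pooled tafamidis against placebo, each stratified by genotype and NYHA class (I/II, III).
3. For each region report net benefit, (wins − losses) / number of tafamidis-placebo pairs within strata, with its standard error or 95% interval. Report the difference NB_US − NB_ex with 95% interval: difference ± 1.96 × √(SE_US² + SE_ex²).
4. State that the estimates and intervals are the main output, and that a non-significant difference is not evidence of consistency.
5. Add a region column to Table 2, marked for the primary row.

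The cost is SAP wording and a few table rows from existing code. SAP section 1 records the study as ongoing and blinded, so this can still be pre-specified. The price is imprecision: under the assumed mix, the smallest region-by-genotype-by-NYHA cell has about 400 × 0.5 × 0.5 × 0.3 = 30 subjects, although the planned eight-stratum test already uses the same cells. Difference tests for genotype and NYHA are optional and not part of this point.
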